6.3 Timing and frequency of analyses

A single principal analysis is anticipated at 15 months after the last man is recruited (at month 48). The Data Monitoring Committee will determine the frequency of confidential interim analyses, but at present these are planned on three occasions during the data collection period (at months 16, 28 and 35).

6.4 Planned secondary subgroup analyses

The two populations of men (having radical prostatectomy or transurethral resection) will be analysed as separate trials as shown above in section 6.1.

Subgroup analyses (separately for the two populations) will explore the effect on urinary incontinence at 12 months after randomisation of:

1. pre-existing urinary incontinence (before prostate surgery)
2. age (up to 70, 71 and over)
3. type of incontinence at trial entry (stress, urge, mixed, other)
4. body mass index up to 30, 30–34.9, 35 or greater
5. centres with and without biofeedback machines
6. type of therapist (physiotherapist or nurse)
7. other morbidity/treatment for other morbidity

Stricter levels of statistical significance ($2p < 0.01$) will be sought, reflecting the exploratory nature of these analyses.

All study analyses will be according to a statistical analysis plan that will be agreed in advance by the MAPS Steering Committee.

6.5 Economic analysis

Both trials (radical prostatectomy or transurethral resection of prostate) will include a formal economic evaluation. Resource use and costs will be estimated for every trial participant. Resource-use data collected will include the intervention and the use of primary and secondary NHS services by the men including referral for specialist management. Personal costs to the men (such as use of pads or work/social restrictions) will also be described. Thus the point of view adopted is that of the NHS and the patient.

6.5.1 Collection of data

At each time point of contact during the study (baseline and 3, 6, 9 and 12 months after randomisation), men will provide information about their use of health services

(via the health care utilisation questions, Appendix VI). At baseline, 6 and 12 months, they will complete the SF-12 and EQ-5D. Midway through the trial (at 6 months after randomisation), a questionnaire survey of all men will be used to ascribe costs to typical episodes of such health service use (the Health Care Unit Cost Questionnaire, Appendix VI). The underlying aim is to keep economic data collection as parsimonious as possible to minimise the burden on the men and the effect on response rates.

6.5.2 Participant costs of urinary incontinence

Participant costs will comprise three main elements: self-purchased health care; travel costs for making return visit(s) to NHS health care; and time costs of travelling and attending NHS health care.

- Self-purchased health care is likely to include items such as pads bought by the participant, prescription costs and over-the-counter medications. Information about these will be collected through the health care utilisation questions (see 6.5.1 above).
- Estimation of travel costs requires information from participants about the number of visits to, for example, their GP or physiotherapist (estimated from the health care utilisation questions) and the unit cost of making a return journey to each type of health care provider (from the Participant Unit Cost Questionnaire, Appendix VI).
- The cost of participant time will be estimated in a similar manner. The participant will be asked, in the Participant Unit Cost Questionnaire, how long they spent travelling to and attending their last visit to each type of health care provider. Participants will also be asked what activity they would have been undertaking (e.g. paid work, leisure, housework) had they not attended the health care provider. These data will be presented in their natural units, e.g. hours, and also costed using standard economic conventions, e.g. the Department of Transport estimates for the value of leisure time. These unit time costs, measured in terms of their natural and monetary terms, will then be combined with estimates of number of health care contacts derived from the health care utilisation questions.

6.5.3 Costs of intervention

Health service costs incurred as the consequence of the intervention will be recorded prospectively for every participant in the study. Main areas of costs will be: staffing (four sessions with the therapist), capital costs (buildings and equipment), and consumables (probes for biofeedback, pads).

6.5.4 NHS costs of other health services used

- Consumables (drugs, pads, etc.)
- Staff time (GP, nurse, consultants)
- Outpatient visits
- Hospital admissions (operations, other)

6.5.5 Cost-effectiveness

Effectiveness within the trials will be measured in terms of quality-adjusted life-years (QALYs) and subjective continence at 12 months (assessed using data from the ICI questionnaire). QALYs will be estimated by combining estimated quantity of life, with quality of life derived from the EQ-5D questionnaire (administered at baseline, 6 and 12 months) and UK tariffs. The estimation of QALYs will take account of the mortality of study participants. Participants who die within the study follow-up will be assigned a zero utility weight from their death until the end of the study follow-up. QALYs before death will be estimated using linear extrapolation between the QALY scores at baseline and all available EQ-5D scores up to death. The method of eliciting QALYs described is one commonly adopted in economic evaluation.

The primary analysis is based on the 1-year follow-up of the trial and two outcomes have been specified. These are incremental cost per additional man continent and incremental cost per QALY. The former outcome has been chosen to facilitate understanding of the findings amongst health care professionals while the second measure, the primary economic outcome, has been chosen to reflect a societal decision-making perspective. The results will be presented as point estimates of mean incremental costs, proportion of men continent, QALYs, and cost per man continent or per QALY. Measures of variance for these outcomes are likely to involve bootstrapping estimates of costs, proportion of men continent, QALYs, and incremental cost per additional man continent and per QALY. Incremental cost-effectiveness data will be presented in terms of cost-effectiveness acceptability curves (CEACs).

Other forms of uncertainty, e.g. concerning the unit cost of a resource, will be addressed using standard deterministic sensitivity analysis. The results of the sensitivity analyses will also be presented as CEACs. Further sensitivity analysis will be conducted to consider the effect of differential timing over which treatments may be given. These data are likely to prove useful for the economic model.

6.5.6 Modelling

While the within study results will prove useful it is important to note that incontinence is a chronic condition and the effects of treatment on costs and outcomes may persist into the future. Therefore, assuming that one intervention is not dominant (less costly but more effective at 12 months), additional useful information for policy makers will be derived from an economic model that considers a longer time horizon. In the model, the findings of the trial will be extrapolated to the patient's lifetime. The model will describe the change in levels of incontinence over the patient's lifetime following the start of treatment. The structure of the model will be developed in collaboration with clinicians and trial collaborators, and parameter estimates for costs and utilities will be derived from the trial data.

In order to extrapolate estimates of cost-effectiveness to a longer time horizon (e.g. the participant's lifetime) than that considered by the trial, a modelling exercise will be developed. The model will be populated using individual patient data from the study as well as both published and unpublished evidence in the field. The methods used to assemble additional data will follow recognised methodology, which will vary according to the type of parameter, extent of uncertainty and role within the model. Therefore, comprehensive systematic searching will be limited to those parameters to which the results of the model are likely to be particularly sensitive. The modelling exercise will comply with recent recommendations on good practice for modelling¹⁴ and the results will be presented in terms of incremental cost per continent man and incremental cost per QALY gained.

Estimates of mortality will be based on data from life tables. As the model will be constructed to estimate outcomes both for men with benign disease and for men with prostate cancer, mortality rates will be adjusted, where necessary, using relative risks of mortality for prostate cancer. These data will be obtained from the literature and from an on-going study within the Health Economics Research Unit in Aberdeen that is looking at the cost-effectiveness of screening for prostate cancer.

Outcomes in the model will be expressed in terms of an incremental cost per QALY. Parameter uncertainty will be integrated by the incorporation of probability distributions into the model and involving Monte Carlo simulation. Other forms of uncertainty such as that associated with choices made about the structure of the model, discount rate, etc., will be addressed through sensitivity analysis. The base-case and sensitivity analyses will be presented as CEACs.

7. SAMPLE SIZE AND FEASIBILITY

7.1 Sample size sought

Based on the aim to detect a difference between intervention and control groups of 15% (70% to 85%) in the number of men no longer incontinent, we will need 174 men per arm of the trial to give 90% power to detect a significant difference at the 5% level. This will allow detection of a difference of 0.30 of a standard deviation at 80% power for continuous measures such as quality of life. Should the proportion of men no longer incontinent be less than 70% we shall still have 80% power to detect a 15% change from 60% to 75%.

Table 1 below is an extrapolation to show the number of men who will need to be approached and hence the number of 'typical sized' clinical centres that will be required. Allowing for a 13% dropout rate after enrolment in the RCT, we plan to recruit 200 men per arm. There will thus be 400 men in each of the two parallel trials who would come from 615 incontinent men assuming that 65% agree to join the trial. Based on conservative assumptions of 50% and 5% incontinent at 6 weeks after radical prostatectomy and endoscopic resection of prostate, respectively, and 80% response rates to the screening questionnaire, 1,540 and 15,400 men will need to be approached. If a typical centre undertakes 30 radical prostatectomies and 300 endoscopic resections of prostate each year, about 26 centres will be required for each trial recruiting over an average of 2 years.

In summary, Table 1 shows that we will need to screen around 17,000 men in Stage 1 of the study, making conservative assumptions about likely response and participation rates. Based on these figures, a 2-year recruitment period in 26 centres will be needed.

Table 1 Recruitment numbers needed

	Radical prostatectomy	Transurethral resection
Men needed per arm (minimum)	174	174
Allowing for 13% dropout	200	200
Total men needed in two arms	400	400
Assuming 65% willing to enter RCT, no. incontinent men needed	615	615
% incontinent at 6 weeks (Stage 2)	50%	5%
No. of men needed to reply to survey	1230	12,300
Assuming 80% response to survey, no. needed for survey (Stage 1)	1540 (approx)	15,400 (approx)
No. of operations per typical centre	30	300
No. of typical centres needed in 2 years	26	26

[figure not shown]
7.2 Recruitment rates

Figure 1 shows the projected recruitment of centres and participants, and projected number of men who would be approached. Three centres will be established relatively early in the project (by 5 months) followed by roll-out to the others over the subsequent 10 months.

The participant recruitment graph in Figure 1 has been modelled to take into account: the phased roll-out to the centres over the first 15 months; that there will be lags between the approach to men when they are in hospital and the despatch of the 'screening' questionnaire and between the despatch of the screening questionnaire and trial recruitment; and that there are likely to be fewer prostatectomies around August and over Christmas (due to holidays). Recruitment continues after the final

screening questionnaires have been sent out because of these 'lags'. The lines for the two trials (radical prostatectomy and endoscopic resection of prostate) are superimposed because their rates of recruitment are expected to be similar.

Figure 1 Projected recruitment chart

In summary, we originally aimed to recruit an average of 8 men to the randomised trial per week over a 2-year period. We estimated that if we had 26 centres, that would have amounted to 30 men per centre in 2 years, half of whom (around 15 in 2 years, or 8 per year) will be randomised to active therapy. In order to achieve this, we estimated that approximately 7 men per centre will need to be screened each week for 2 years. As the recruitment period was extended by 9 months in May 2007 (by the HTA) recruitment targets have altered since these original projections –the graph above therefore now reflects both the original and the extended recruitment periods.

8 ORGANISATION

A detailed plan and timetable of study organisation is given in the Gantt chart (Appendix VIII). In summary, it is as follows – 1–4 months: set up office, assemble team, and establish first centre; 5–15 months: establish study in all 26 centres; 5–36 months: identify and recruit 800 men with urinary incontinence (average 24 months in each centre); 13–48 months: follow up at 6 and 12 months after randomisation; 49–54 months: complete data collection, analysis and dissemination. In the light of the revised recruitment period (the 9-month extension) the Gantt chart has also been revised (Version 6 protocol).

The Gantt chart also shows when we expect the major study events to occur, including recruitment, study progress and meetings. There will be 3-monthly project management meetings, five meetings of the Steering Committee and four of the Data Monitoring Committee. Two meetings are planned for collaborators (including urologists, therapists, local recruitment officers and consumer participants), the first timed to occur when all the sites have been identified and the second when results are available. Four Training Meetings will be held to train the therapists during the course of the first year. Remote training of any other thepaists unable to attend these days will occur as and when applicable.

Based on this chart, the specific, time-related milestones given in Appendix VII will be used to allow close monitoring of progress.

8.1 Local organisation in centres

i) Lead Urologist (Local Principal Investigator)

Each collaborating centre will identify a Lead Urologist who will be the point of contact for that centre. The responsibilities of this person will be to:

- establish the study locally [for example by getting agreement from clinical colleagues; facilitate local research ethics committee approval (LREC); liaise with R&D department; identify and appoint a local Recruitment Officer; and inform all relevant local staff about the study (e.g. secretaries, ward staff)]
- take responsibility for clinical aspects of the study locally (for example if any particular concerns occur)
- notify the Study Office of any unexpected clinical events which might be related to study participation
- provide support and supervision for the local Recruitment Officer
- represent the centre at the collaborators' meeting

ii) Local Recruitment Officer

Each collaborating centre will appoint a local Recruitment Officer to organise the day-to-day recruitment of men to Stage 1 of the study (the Screening Survey). The responsibilities of this person will be to:

- keep regular contact with the local Lead Urologist, with notification of any problem or unexpected development
- maintain regular contact with the Study Office
- keep local staff informed of progress in the study
- contact potential participants by: organising mailing out of the Patient Information Sheet to men being admitted electively for prostate surgery; identifying all eligible men on the ward while they are in hospital for their prostate surgery; explaining the screening study and the potential for participation in a trial if they are incontinent after surgery; explaining what is intended by research access to their NHS data; and describing the possibility of long-term follow-up whether or not they are incontinent
- obtain the men's written consent to being sent a screening questionnaire
- keep a log of whether eligible men are recruited or not (with reasons for non-participation) (Appendix I)
- collect baseline data describing the men (Appendix I), and send these to the Study Office along with the signed consent forms (Appendix I)
- organise and supervise alternative recruiters in case of holiday or absence
- represent the centre at the collaborators' meeting

iii) Therapists and training

Each collaborating centre will identify a Lead Therapist who will be responsible for co-ordinating the active intervention at a local level. (S)he will identify the local therapist who will carry out the intervention, or may assume this role personally. The therapist may be a specialist physiotherapist or continence nurse specialist. The therapist will attend a Training Day (led by [name]) to ensure consistency of training and intervention in each centre. There will be four Training Days at a range of locations throughout the UK during the setting-up phase of the study.

The therapist will use standard study instruction materials and documentation, which will be provided by the Study Office. The Study Office will also be the first point of contact for the therapist in case of problems, concerns, adverse effects or need for advice.

The responsibilities of the therapist will be to:

- attend a training day to become familiar with the standard method of teaching the men and the standard study documentation
- contact men allocated to the active arm by sending them an initial appointment (for one hour), and repeat three-quarter-hour appointments at 2, 6 and 12 weeks thereafter
- notify the Study Office if men fail to attend: a phone number will be provided for this purpose
- notify the Study Office of any unexpected clinical events which might be related to study participation
- teach all the men pelvic floor muscle training, using digital anal biofeedback to reinforce correct contractions
- use machine biofeedback with an anal probe if, in their opinion, it is clinically indicated (and a machine is available)
- teach bladder training to men who have urge incontinence
- provide other lifestyle advice as appropriate
- record the details of the treatment and response to treatment at each visit using standard study documentation (assessment and treatment forms, Appendix V)
- return the assessment and treatment forms to the Study Office at the end of each man's 3-month treatment period
- support the men in adhering to treatment
- represent the centre at the collaborators' meeting

iv) *Other training materials*

We hope also to provide an interactive CD-rom instruction and reminder package both to supplement the main Training Day teaching, and in case some therapists cannot attend or if staff changes result in new therapists being appointed.

It may be possible to amend this material for use in training other NHS staff after the trial is finished if the intervention is effective.

8.2 Study co-ordination in Aberdeen

i) *The Study Office Team*

The Study Office is in the Health Services Research Unit in Aberdeen and provides day-to-day support for the clinical centres. It is responsible for all data collection (such as mailing questionnaires), follow-up, data processing and analysis. It is also responsible for randomisation, despatch of Lifestyle Booklets and communicating with the therapists about men allocated to active treatment. Finally, we intend to produce a yearly MAPS Newsletter for participants and collaborators to inform everyone of progress and maintain enthusiasm.

The MAPS Study Office Team will meet formally at least monthly during the course of the study to ensure smooth running and trouble-shooting.

ii) *The Project Management Group*

The study is supervised by its Project Management Group. This consists of the grant holders and representatives from the Study Office. Observers may be invited to attend at the discretion of the Project Management Group. We plan to meet every 3 months on average.

iii) *The Steering Committee*

The study is overseen by an independent Steering Committee. The Chairman is [name], with [name] and [name] as other independent members appointed by the HTA. The other members are the grant holders. Observers or members of the host university (Aberdeen) and the funders (the HTA) may also attend, as may other members of the Project

Management Group or members of other professional bodies at the invitation of the Chair.

8.3 Research Governance, EU Directives, Data Protection and Sponsorship

i) Research Governance, EU Directive

The trial will be conducted in compliance with the EU Clinical Trials Directive (EU-CTD, 1 May 2004) although it does not come within the scope of the Directive. Other studies associated with the trial will either be conducted in compliance with the EU Clinical Trials Directive (1 May 2004) or in line with local implementation of Research Governance to at least the standard of the Aberdeen University policy on Research Governance (<http://www.abdn.ac.uk/iahs/research-governance/index.shtml>).

ii) Sponsorship

Before April 2007 the sponsorship for these studies (RCT and observational) was the Department of Health, UK. Their duties as sponsors were co-ordinated through the National Coordinating Centre for Health Technology Assessment (NCCHTA) in Southampton. In April 2007 sponsorship responsibility was transferred from the NCCHTA to the host institution, the University of Aberdeen.

Responsibility for transacting Part 3 of the EU-CTD (study initiation and finance), Part IV (Compliance with Good Clinical Practice) and Part V (Pharmacovigilance) will be delegated to the Chief Investigators, [name] [name] and [name] at Aberdeen University. They will ensure, through the Steering Committee, that adequate systems are in place for monitoring the quality of the study (compliance with GCP) and appropriate expedited and routine reports of adverse effects, to a level appropriate to the risk–benefit assessment of the trials.

iii) Data Protection

All data collected and stored within the study will comply with the Data Protection Act.

8.4 Data and safety monitoring

i) Data Monitoring Committee

A Data Monitoring Committee (DMC) will be established. This will be independent of the study organisers. During the period of recruitment to the study, interim analyses will be supplied, in strict confidence, to the Data Monitoring Committee, together with any other analyses that the committee may request. This may include analyses of data from other comparable trials. In the light of these interim analyses, the Data Monitoring Committee will advise the Steering Committee if, in its view:

- a) the active intervention has been proved, beyond reasonable doubt,* to be different from the control (standard management) for all or some types of men, and
- b) the evidence on the economic outcomes is sufficient to guide a decision from health care providers regarding recommendation of this service development.

The Steering Committee can then decide whether or not to modify intake to the trial. Unless this happens, however, the Steering Committee, Project Management Group, clinical collaborators and study office staff (except those who supply the confidential analyses) will remain ignorant of the interim results.

The frequency of interim analyses will depend on the judgement of the Chairman of the Committee, in consultation with the Steering Committee. However, we anticipate that there might be three interim analyses and one final analysis.

* Appropriate criteria for proof beyond reasonable doubt cannot be specified precisely. A difference of at least three standard deviations in the interim analysis of a major end point may be needed to justify halting, or modifying, such a study prematurely (Peto R et al., *Br J Cancer* 1976;34:548–612).

The Chairman is [name], with [name], [name] and [name] as other independent members, to be appointed after confirmation by the HTA.

ii) Safety concerns

The MAPS trial involves conservative interventions which are well established in clinical practice, although unproven regarding effectiveness for men after prostatectomy. We do not anticipate any adverse effects, but would respond appropriately to any notification.

Collaborators and participants may contact the chairman of the Steering Committee through the Study Office about any concerns they may have about the study. If concerns arise about procedures, participants or clinical or research staff (including risks to staff) these will be relayed to the Chairman of the Data Monitoring Committee.

As the trial arm to which men are allocated cannot be blind after randomisation has occurred, unblinding is not an issue in this trial.

The Multicentre Research Ethics Committee for Scotland has approved the study for the UK (ref MREC/04/10/01). The study will be conducted according to the principles of good practice provided by Research Governance Guidelines.

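### Section 8.4 i ties DMC advice to sufficient economic evidence in both directions, so interim evidence that active therapy is inferior or harmful does not by itself trigger advice

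*Protocol*

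**What the plan says.** Section 8.4 i of the protocol says that, in the light of the interim analyses, "the Data Monitoring Committee will advise the Steering Committee if, in its view", two listed conditions hold.

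- Condition (a) is that the active intervention has been proved "to be different from the control (standard management) for all or some types of men, and".
- Condition (b) is that "the evidence on the economic outcomes is sufficient to guide a decision from health care providers regarding recommendation of this service development".

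The consequence follows: "The Steering Committee can then decide whether or not to modify intake to the trial". So does the default: "Unless this happens, however, the Steering Committee, Project Management Group, clinical collaborators and study office staff", apart from those who prepare the confidential analyses, are not told the interim results.

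A footnote concedes that the standard of proof in (a) cannot be fixed exactly. As a guide to when early action is warranted, it offers this: "A difference of at least three standard deviations in the interim analysis of a major end point may be needed to justify halting, or modifying".

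Section 8.4 ii expects no adverse effects. It says of concerns about procedures, participants or staff that "these will be relayed to the Chairman of the Data Monitoring Committee". It does not say when the DMC then advises the Steering Committee.

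On the economic side, section 6.5.5 states: "The primary analysis is based on the 1-year follow-up of the trial". Section 6.3 plans interim analyses at months 16, 28 and 35.

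**The concern.** Condition (a) has no direction, so a proven deficit on active therapy falls under it just as a proven benefit does. Condition (b) is written with adoption in mind. It is a sensible extra hurdle before recruitment is cut short because the service works. It is not a sensible hurdle before the Steering Committee is told that men given the service do worse.

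The sentences that follow make this matter. The Steering Committee is the body that can change intake, and the joint condition is the only route stated in section 8.4 i by which comparative interim results reach it. A between-arm deficit in continence or bowel function (both outcomes in section 6.2) may be visible only in that comparison, which outside the DMC only the staff who prepare the confidential analyses see.

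**Working it through.** **Step 1: the rule as logic.** Let A be proof of a difference and B be sufficient economic evidence. The text gives advice when A and B both hold.

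| Direction of A | B met? | Advice triggered as written? |
|---|---|---|
| Favours active | Yes | Yes |
| Favours active | No | No (a deliberate and reasonable hurdle) |
| Against active | Yes | Yes |
| Against active | No | No (the gap) |

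Only the last row is at issue.

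**Step 2: do other provisions fill that row?**

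- Section 8.4 ii carries concerns to the DMC Chairman. It gives no rule for advice from the DMC onward.
- Section 8.3 ii provides for expedited and routine reports of adverse effects. Sections 4.2 and 8.1 have GPs, lead urologists and therapists notify the Study Office. These routes carry individual events, not the comparison between arms.
- Appendix XI (terms of reference for the two committees) is listed in the contents but is not available here. It may contain a harm provision.

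In the text available, the row stays open for comparative interim results.

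**Step 3: how strong would the evidence under (a) be?** The protocol's only figure is the guide of three standard deviations. Two-sided, p = 2 × (1 − Φ(3)) = 0.0027. Take 70% continence in the control group (section 7.1), n men per arm and a deficit d on active. The mean proportion is p̄ = 0.70 − d/2 and z = d / √(2p̄(1 − p̄)/n). For n = 100 and d = 0.209: p̄ = 0.5955, standard error = √(2 × 0.5955 × 0.4045 / 100) = 0.0694, z = 3.01. The deficits needed for z = 3 are:

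| Men per arm with data | Deficit needed (percentage points) |
|---|---|
| 50 | 30 |
| 100 | 21 |
| 150 | 17 |
| 200 | 15 |

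Even a deficit of this size would not meet the written rule without B.

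**Step 4: how many men could be affected?** The protocol gives no accrual table in the text, so this rests on assumptions:

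- Centres rise linearly from 3 at month 5 to 26 at month 15 (section 7.2).
- Recruitment is proportional to open centres, with a lag L of 1 to 3 months to randomisation.
- Each trial reaches 400 men at month 36 (section 8), or at month 45 if the nine-month extension is added.
- The looks stay at months 28 and 35.

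Centre-months to month 15 are 10 × (3 + 26)/2 = 145, then 26 a month. Months 28 to 35 contribute 7 × 26 = 182.

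| End of recruitment | L (months) | Total centre-months | Men per trial randomised, months 28–35 |
|---|---|---|---|
| 36 | 1 | 145 + 26 × 20 = 665 | 400 × 182/665 = 109 |
| 36 | 3 | 145 + 26 × 18 = 613 | 400 × 182/613 = 119 |
| 45 | 1 | 145 + 26 × 29 = 899 | 400 × 182/899 = 81 |
| 45 | 3 | 145 + 26 × 27 = 847 | 400 × 182/847 = 86 |

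Men with 12-month data at month 28 are those randomised by month 16. The centre-months behind them are 145 (L = 1) or 8 × (3 + 21.4)/2 = 97.6 (L = 3). That gives 400 × 97.6/847 = 46 at the lowest and 400 × 145/665 = 87 at the highest, or about 23 to 44 per arm before dropout. On 12-month continence, a three-standard-deviation deficit at that look would have to exceed 30 points. An earlier signal would more likely come from the 3-, 6- or 9-month outcomes.

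**The case against.** The strongest reply is that the text obliges advice in one situation without forbidding it in others. It does not say only if, it leaves the matter to the DMC's view, and it lets the DMC ask for further analyses. A reader might infer that a DMC convinced of harm must stay silent. The documents do not go that far. What stands against the reply is the default sentence, which keeps the Steering Committee uninformed unless the stated event occurs. A DMC that spoke up on harm alone would have to act outside the written rule.

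Second, (b) may be easy to meet when active therapy is worse. A decision not to recommend a service is still a decision, and active therapy adds four therapist sessions. An arm that is worse and costs more is dominated, and no precise ratio is needed to say so. This has force: it shortens any delay. It still depends on how the DMC chooses to read a condition framed around recommendation.

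A reader might infer three further things that do not hold:

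- *That (b) must wait for the lifetime model.* Section 6.5.6 calls for the model when neither arm dominates, so a worse and costlier active arm removes that reason for it.
- *That the month-16 look shows (b) blocking a warning.* No man has 12-month data then, so (a) on the primary outcome is blocked just as (b) is. The economic and clinical primary outcomes share the one-year horizon.
- *That adverse effects are held back by this rule.* They have the separate routes in step 2, and allocation is not blinded.

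Finally, Appendix XI is the natural home for a harm provision and has not been seen.

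**Conclusion.** The point holds in a limited form. As section 8.4 i is written, comparative interim evidence that active therapy is inferior or harmful does not trigger advice to the Steering Committee until the economic condition is also met. Nothing else in the protocol text available covers that case.

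The practical risk is modest. The therapy is conservative, no adverse effects are expected, the DMC has discretion, and a dominated arm might satisfy (b) quickly. The 81 to 119 men per trial randomised between months 28 and 35 are not an estimate of men harmed by the wording. They become relevant only if inferiority were convincing at month 28 while the economic evidence was not, and the documents do not show that to be likely. No sample size, power or analysis figure changes.

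This is a minor to moderate correction. It rests on the literal reading of the two joined conditions and on Appendix XI not already providing for harm.

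**What to change.** Reword section 8.4 i so that the economic condition applies in one direction only. The DMC would advise the Steering Committee if, in its view, either:

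1. a difference in favour of active therapy is established to the present standard and the economic evidence is sufficient; or
2. there is a difference against active therapy, for all or some types of men, whatever the state of the economic evidence.

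Leave the strength of evidence in the second limb to the DMC's judgement, as now. Replacing the present standard with a lower threshold for harm would be a separate and debatable change, and this point does not need it.

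Check Appendix XI and align the DMC terms of reference. If they already contain a harm provision, a cross-reference from section 8.4 is enough.

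The cost is about one sentence in each document. It needs no further data or men, does not alter the type I error, and leaves the criterion for early action on benefit unchanged.
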